6.3.3 Vital Signs

Vital sign assessments will be performed each day the patient is in the index hospital. Observed values and changes from baseline in each vital sign parameter will be summarized by study day and reported by treatment arm. Vital sign parameters include: weight (kg, screening only), height (cm, screening only), BMI (kg/m², screening only), systolic and diastolic blood pressure (mmHg), respiratory rate (breaths/m), heart rate (beats/min) and body temperature (F).

6.3.4 Electrocardiogram

Electrocardiogram (ECG) may be performed throughout the time the patient is in the index hospital as part of routine care. ECGs will be performed at screening, on Day 28 and Day 40. If these visits are conducted remotely, the ECG may be omitted.

Data collected in the eCRF includes the overall evaluation of the ECG, either normal, abnormal and not clinically significant or abnormal and clinically significant. Listings of data collected will be provided by patient.

6.3.5 Physical Examinations

Physical examinations will be collected as per standard of care and details are not collected on the CRF. Any abnormal and clinically significant findings will be captured as AEs and reported as such.

6.3.6 Other

6.3.6.1 Non-mechanical ventilation

Use of non-mechanical ventilation is assessed each day the patient is in the index hospital. The number and percentage of patients with non-mechanical ventilation use, the delivery system used and the total number of days with non-mechanical ventilation use will be summarized by treatment arm. All data will be provided in by-patient listings.

6.3.6.2 Chest Imaging

Lung imaging (X-ray, MRI, or CT) will be performed at screening to confirm pulmonary disease due to COVID-19. Imaging may also be performed throughout the time the patient is in the index hospital as deemed clinically relevant for standard of care. Images post-study treatment will be evaluated for any changes (same, worsening, improvement) compared with a previous image and data will be provided in a by-patient listing. Images that worsen compared with a previous image will be flagged in the listing.

6.3.6.3 SaO₂

Room air SaO₂ will be collected at screening, at hospital discharge, Day 28 and Day 40. Observed values and changes at each timepoint of collection will be reported. Collection of SpO₂ on room air at sea level and PaO₂/FiO₂ will be listed. All data will be included in patient listings.

6.3.6.4 Anti-drug Antibody

The development of anti-drug antibodies will be assessed. Blood samples will be collected prior to dosing with study treatment and at the Day 28 and Day 40 visits and will be analyzed at a central laboratory. A listing of anti-drug antibody data will be provided.

6.3.6.5 TNF Blood Levels

Blood samples to assess TNF levels will be collected on Day 1 prior to dosing with study treatment. Results will be included in patient a listing.

7 APPENDICES

7.1 APPENDIX 1: Partial Date Conventions

ALGORITHM FOR TREATMENT EMERGENCE OF ADVERSE EVENTS:

START DATE	STOP DATE	ACTION
Known	Known/Partial/ Missing	If start date < study drug start date, then not TEAE If start date >= study drug start date, then TEAE *if time is collected, consider time in determining if event is a TEAE
Partial, but known components show that it cannot be on or after study drug start date	Known/Partial/ Missing	Not TEAE
Partial, could be on or after study drug start date	Known	If stop date < study drug start date, then not TEAE If stop date >= study drug start date, then TEAE *if time is collected, consider time in determining if event is a TEAE
	Partial	Impute stop date as latest possible date (i.e., last day of month if day unknown or 31st December if day and month are unknown), then: If stop date < study drug start date, then not TEAE If stop date >= study drug start date, then TEAE
	Missing or ongoing is checked	TEAE
Missing	Known	If stop date < study drug start date, then not TEAE If stop date >= study drug start date, then TEAE *if time is collected, consider time in determining if event is a TEAE
	Partial	Impute stop date as latest possible date (i.e., last day of month if day unknown or 31st December if day and month are unknown), then: If stop date < study drug start date, then not TEAE If stop date >= study drug start date, then TEAE
	Missing or ongoing is checked	TEAE

ALGORITHM FOR PRIOR / CONCOMITANT MEDICATIONS:

START DATE	STOP DATE	ACTION
Known/Partial/Missing	Known	If stop date < study drug start date, assign as prior If stop date >= study drug start date, assign as concomitant
	Partial	Impute stop date as latest possible date (i.e., last day of month if day unknown or 31 st December if day and month are unknown), then: If stop date < study drug start date, assign as prior If stop date >= study drug start date, assign as concomitant
	Missing	If stop date is missing, assign as concomitant If “Ongoing” is flagged, assign as concomitant

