7.1.9 Adverse Events

7.1.9.1 Definition of Adverse Events

An AE is defined as any untoward medical occurrence in a clinical study participant administered a medicinal product which does not necessarily have a causal relationship with this treatment. An AE can therefore be any unfavourable and unintended sign (including an abnormal laboratory finding), symptom, or disease temporally associated with the use of a medicinal (investigational) product, whether or not it is related to the medicinal (investigational) product. This includes an exacerbation of pre-existing conditions or events, intercurrent illnesses, drug interaction or the significant worsening of the indication under investigation that is not recorded elsewhere in the CRF under specific efficacy assessments. Anticipated fluctuations of pre-existing conditions, including the disease under study that do not represent a clinically significant exacerbation or worsening need not be considered AEs.

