7.1.9.5 Recording of Adverse Events

Adverse Events will be recorded and reported from the study enrolment until Study Day 70 for all participants who are randomized. Refer to [Section 7.1.9.1](#) for definition of AEs.

When an AE/SAE occurs, it is the responsibility of the investigator to review all documentation (eg, hospital progress notes, laboratory, and diagnostic reports) relative to the event. The investigator will then record all relevant information regarding an AE/SAE in to the CRF. All

CONFIDENTIAL

details of any treatments initiated due to the AE should also be recorded in the participants' notes and the CRF.

Each AE will be documented in the participant's CRF. If an AE changes in frequency or intensity during a study, a new entry of the event must be made in the CRF.

The investigator will attempt to establish a diagnosis of the event based on signs, symptoms, and/or other clinical information. In the absence of a diagnosis, the individual signs/symptoms should be documented.

All AEs occurring during the study must be documented on the relevant CRF pages. The following data should be documented for each AE:

- Description of the symptom event;
- Classification of 'serious' or 'not serious';
- Severity - graded according to the CTCAE v5.0;
- Date of first occurrence and date of resolution (if applicable);
- Action taken;
- Causal relationship;
- Outcome of event (unknown, recovered, not yet recovered, recovered with sequelae, death) [with date and cause reported].

After the initial AE or SAE report, the investigator is required to proactively follow each participant and provide further information to the sponsor on the participant's condition.

All AEs are required to be assessed by a medical practitioner. All AEs or SAEs documented at a previous visit/contact that are designated as ongoing, will be reviewed at subsequent visits/contacts. All AEs or SAEs assessed as related to IP will be followed until Study Day 70. The investigator will ensure that follow-up includes any supplemental investigations as may be indicated to elucidate the nature and/or causality of the AE or SAE.

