5.3 Data Imputation Rules

Generally, missing data will not be imputed, and will be presented as collected in the study database.

In cases where AE or medication dates are missing, the imputation methods described in Appendix 1 will be used to determine flags for treatment-emergent events and concomitant medications.

For interim reporting purposes or ongoing reporting needs, treatment or study end dates will be imputed as the earliest of the data cutoff date, date of death, or date of treatment study withdrawal.

Other missing data methods specific to statistical analysis will be proposed within the respective analysis section, as needed.

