6.3.1 Adverse Events

Adverse events (AEs) will be recorded from study enrolment until study Day 70. AEs will be assessed for severity according to the Common Terminology Criteria for Adverse Events (CTCAE) v5.0, relationship to study drug, and seriousness. Adverse events will be considered treatment-emergent if the event was a pre-existing condition that increases in severity, becomes serious after start of study treatment, or if the onset of the event occurs after the first dose of study treatment. Any missing severity assessments will be assumed as Grade 3 severity and missing relationship assessments will be assumed as related.

An overview of treatment-emergent AEs (TEAEs) will be provided, including counts and percentages of patients with any incidences of: TEAEs, TEAEs related to study treatment, serious adverse events (SAEs), TEAEs leading to study discontinuation, SAEs, and fatal SAEs.

Adverse events will also be displayed by MedDRA coded system organ class (SOC) and preferred term (PT) in descending order of overall incidence. Data will be reported by treatment arm and overall.

Summaries of adverse events by SOC and PT will be provided for the following:

- TEAEs;
- TEAEs related to study treatment;
- CTCAE Grade 3 or higher TEAEs;
- CTCAE Grade 3 or higher TEAEs related to study treatment;
- SAEs; and
- TEAEs leading to study discontinuation.

When calculating the incidence of AEs, each AE will be counted only once for a given patient within a MedDRA category (e.g. overall, system organ class or preferred term). When AEs are summarized within levels of another AE assessment (e.g., relatedness or severity), AEs will be counted once per patient at the worst level of the assessment (e.g., strongest relationship to study drug or greatest severity).

A comprehensive listing of all AEs reported will be provided in a by-patient data listing. In addition, the following listings will be provided:

- TEAEs related to study treatment;
- SAEs;
- TEAEs leading to study discontinuation; and
- Fatal AEs.

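### The SAP's Appendix 1 flags events known to start before dosing as not treatment-emergent without the worsening and seriousness checks that SAP 6.3.1 requires

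*SAP*

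**What the plan says.** SAP 6.3.1 gives three routes to treatment-emergent status. Two concern events already present at dosing: a "pre-existing condition that increases in severity, becomes serious after start of study treatment". The third is onset after the first dose.

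SAP Appendix 1 (section 7.1) holds an algorithm for treatment emergence. Two of its rows deal with a start before dosing:

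- Known start date: "If start date < study drug start date, then not TEAE".
- Partial start date described as "Partial, but known components show that it cannot be on or after study drug start date": not treatment-emergent.

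Neither row refers to severity or seriousness. A third group of rows, for a start date that is "Partial, could be on or after study drug start date", is decided on the stop date, and so is a wholly missing start date.

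SAP 5.3 states when the appendix is used: "In cases where AE or medication dates are missing, the imputation methods described in Appendix 1 will be used to determine flags".

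Two protocol rules also bear on the point. Section 7.1.9.5 says: "If an AE changes in frequency or intensity during a study, a new entry of the event must be made in the CRF". Section 7.1.9.1 defines an adverse event and adds: "This includes an exacerbation of pre-existing conditions or events".

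**The concern.** The definition and the algorithm can give opposite flags for the same event. Appendix 1 is the only step-by-step derivation of the flag in the SAP, so a programmer could reasonably implement it as written and never apply two of the three routes in 6.3.1 to an event whose start is known to precede dosing.

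Adverse events are recorded from enrolment, so pre-dose onsets will be in the database. At stake is the consistency of the safety tables. An event that turned serious after study drug could be counted among the SAEs but not among the TEAEs and, if judged related, not in the related-TEAE table or listing either. The algorithm is also less cautious with well-documented events: an ongoing event with no start date defaults to treatment-emergent, whereas one with an exact pre-dose date is rejected whatever happens later.

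**Working it through.** No figure in the plan is under test, so the check traces each type of event through both rules. I read *pre-existing* in 6.3.1 as present before the first dose, because the same sentence sets it against onset after the first dose.

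1. **Start known to precede dosing; event later becomes serious with no change in frequency or intensity.** Under 6.3.1 it is treatment-emergent. Under Appendix 1 it is not. Protocol 7.1.9.5 asks for a new entry only when frequency or intensity changes, so no second record is required. An event can become serious in this way: Protocol 7.1.9.2 includes hospitalisation that the investigator judges longer than expected for COVID-19. The conflict is real.

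2. **Partial start date certain to precede dosing; same later course.** The result is as in case 1.

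3. **Start known to precede dosing; event later increases in severity.** On the original record, 6.3.1 says treatment-emergent and Appendix 1 says not. The protocol requires a new entry, however. If that entry starts on the date of the change, Appendix 1 also returns treatment-emergent and the event is in the tables. If the entry is missing or repeats the original onset date, the conflict remains. The documents do not say which start date the entry carries.

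4. **Medical-history condition that worsens after dosing.** The exacerbation is an adverse event in its own right. If its onset is dated to the worsening, Appendix 1 returns treatment-emergent and there is no conflict.

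5. **True onset before dosing, but the start date is missing or ambiguous.** If the stop date is on or after study drug start, or is missing, or the event is ongoing, Appendix 1 returns treatment-emergent. It therefore does not reject all pre-dose onsets.

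**Which outputs are affected in case 1.** SAP 6.3.1 plans SAE summaries and an SAE listing that are not labelled as treatment-emergent, and a listing of all adverse events. The event stays in those. It is lost from the TEAE table and, if judged related, from the related-TEAE table and listing.

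**Exposure window.** Randomization is within 1 day of screening (Protocol 4.1) and the first dose follows immediately (Protocol 6.3), so a recorded onset between enrolment and dosing falls within about a day.

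**Scale.** The documents give no adverse event rates. The SAP reports 77 participants dosed (6.2.4). One participant is 1/77 = 1.3% of them. If the arms are about equal (an assumption), one participant is 1/38.5 = 2.6% of an arm. A reported incidence moves by that amount only if the participant has no other event in the same category. This is a unit of scale and not an estimate of how many participants are affected.

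**The case against.** The strongest defence is that Appendix 1 was never meant to override 6.3.1. Its title concerns partial dates, and SAP 5.3 invokes it where dates are missing. On that reading, 6.3.1 already governs complete dates. This is a fair account of the likely intent, but it does not settle the matter: the appendix has an explicit row for known start dates, the algorithm is headed as one for treatment emergence, and no text ranks the two sections. It also leaves the second pre-dose row untouched, because that row does deal with partial dates.

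The second defence is that the protocol's recording rules deal with worsening. This largely stands. A reader might infer that worsening events in general drop out of the TEAE tables. The new-entry rule and the exacerbation clause do not support that, provided the record is dated to the change. A reader might also infer that every event with a pre-dose onset is rejected. Case 5 shows otherwise.

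Third, the population's acute illness adds less than it seems to. Protocol 7.1.9.1 leaves out anticipated fluctuations of the disease, and worsening of the indication that is captured under efficacy. Progression to ventilation or death is the primary endpoint. Protocol 9.5.4 describes the events collected as non-disease related. This stands, and it narrows the class of events.

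Fourth, nothing serious disappears from the report, since the SAE table and the listings do not depend on the flag. This stands too. A reader who inferred that serious harm is hidden would be wrong. The defect is an inconsistency between tables.

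**Conclusion.** The point holds in a narrow form. For a start date known, or certain from its known parts, to precede dosing, Appendix 1 contradicts 6.3.1 because it omits the severity and seriousness criteria, and the SAP does not say which section prevails. The firm gap is an adverse event with onset between enrolment and dosing that becomes serious without a change in frequency or intensity. Worsening events join it only where the new CRF entry is absent or carries the original onset date.

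The number affected cannot be estimated from the documents. Any percentage of the 77 dosed participants would be an assumption with nothing in the plan behind it. The number is probably small, because the pre-dose window is about a day and the remaining route is specific. The conclusion rests on reading *pre-existing* as present before the first dose, and on the algorithm being programmed as written. It is a minor defect, but a rule that contradicts the SAP's own definition is worth correcting while amendment is possible.

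**What to change.** In Appendix 1, add to both pre-dose rows (known start, and partial start that must precede dosing): *unless the event increased in severity or became serious on or after study drug start, then TEAE*. Add one sentence to 6.3.1 or to the appendix saying that 6.3.1 governs if the two differ. That is safer than saying the appendix serves only for missing dates, which would leave the amended known-date row with no purpose.

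Two data points need care:

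- The adverse event items in Protocol 7.1.9.5 include a serious or not-serious classification and the dates of first occurrence and resolution, but no date of becoming serious. If the AE page does not hold that date, take it from the SAE form (Protocol 7.1.9.6).
- State in the programming specification which start date a new entry for a changed event carries, and check pre-dose events for missing follow-on entries.

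The cost is a small amount of extra programming and data checking. SAP section 1 allows amendment before final database lock and unblinding. After that, the derivation used should be described in the clinical study report, as SAP 1.1 provides for departures from the plan.

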7.2 APPENDIX 2: Estimand Terminology

Source: ICH E9 R1

Strategy	Description
Treatment policy	The occurrence of the intercurrent event is irrelevant: the value for the variable of interest is used regardless of whether or not the intercurrent event occurs.
Composite Variable	The occurrence of the intercurrent event is taken to be a component of the variable, i.e. the intercurrent event is integrated with one or more other measures of clinical outcome as the variable of interest.
Hypothetical	A scenario is envisaged in which the intercurrent event would not occur: the value to reflect that scientific question of interest is that which the variable would have taken in the hypothetical scenario defined.
Principal stratum	The target population might be taken to be the principal stratum (see Glossary) in which an intercurrent event would not occur.
While on treatment	Response to treatment prior to the occurrence of the intercurrent event is of interest.
